5.3 Immediately Reportable Events

The investigator must immediately report after either the investigator or site personnel become aware of any SAE, AE related to occupational exposure, DILI, or confirmed pregnancy, by telephone, fax, or e-mail to the sponsor using the contact information on the cover page of this protocol. An IRE form must be completed and sent by e-mail to the sponsor. (Please note that the IRE form is NOT the AE CRF.)

Subjects experiencing SAEs should be followed clinically until the events are resolved, stabilized, or the subject is lost to follow-up. Resolution means that the subject has returned to the baseline state of health and stabilized means that the investigator does not expect any further improvement or worsening of the subject's condition. It is expected that the investigator will provide or arrange appropriate supportive care for the subject and will provide prompt updates on the subject's status to the sponsor.

5.4 Potential Drug-Induced Liver Injury

For a subject who experiences an elevation in aspartate aminotransferase (AST) or alanine aminotransferase (ALT) that is ≥ 3 times the upper limit of normal (ULN), a total bilirubin level should also be evaluated. If the total bilirubin is ≥ 2 times the ULN, complete an IRE form with all values listed and also report as an AE on the CRF.

Protocol 156-102-00136

5.5 Pregnancy

Women of child-bearing potential (WOCBP) are defined as female subjects for whom menstruation has started and who are not documented as sterile (ie, have had a bilateral oophorectomy and/or hysterectomy or who have been postmenopausal for at least 12 months).

For men who are sexually active with partners of child-bearing potential, there must be a documented agreement that the subject and/or their partner will take effective measures (ie, double-barrier method) to prevent pregnancy during the course of the trial and for 30 days after the last dose of IMP. Unless the subject is sterile (ie, women who have had a bilateral oophorectomy and/or hysterectomy or who have been postmenopausal for at least 12 consecutive months; or men who have had a bilateral orchidectomy) or remains abstinent, 2 of the following precautions must be used: vasectomy, tubal ligation, vaginal diaphragm, intrauterine device, birth control pills, or condom with spermicide. Any single method of birth control, including vasectomy and tubal ligation, may fail, leading to pregnancy. The contraceptive method will be documented at each trial visit.

During the trial, all subjects should be instructed to contact the investigator immediately if they suspect their partners might be pregnant (eg, missed or late menstrual cycle).

The investigator must immediately notify the sponsor of any pregnancy associated with IMP exposure during the trial and for 30 days after the last dose of IMP, and record the event on the IRE form and forward it to the sponsor. The sponsor will forward Pregnancy Surveillance Form(s) for monitoring the outcome of the pregnancy.

The investigator must report to the sponsor, on appropriate Pregnancy Surveillance Form(s), follow-up information regarding the course of the pregnancy, including perinatal and neonatal outcome. Infants will be followed for a minimum of 6 months from the date of birth.

5.6 Procedure for Breaking the Blind

Not applicable.

5.7 Follow-up of Adverse Events

For this trial, information on AEs will be followed up until discharge in Period 3.

5.7.1 Follow-up of Nonserious Adverse Events

Nonserious AEs that are identified at any time during the trial must be recorded on the AE CRF with the current status noted. If a subject has an AE or has not recovered from an AE at the last scheduled contact, follow-up contacts will be scheduled at least every

Protocol 156-102-00136

4 weeks until the event is resolved, stabilized, or the subject is lost to follow-up. All nonserious events that are ongoing at the last scheduled contact will be recorded as ongoing on the CRF. For any AE having been identified throughout the trial, during analysis, additional relevant medical history information may be requested to further ascertain causality (including, but not limited to, information such as risk-related behavior, family history and occupation). The follow-up information after the last scheduled contact will be recorded in the subject's medical record.

5.7.2 Follow-up of Serious Adverse Events

This trial requires that subjects be actively monitored for SAEs up to discharge in Period 3.

Serious AEs that are **identified or ongoing at the last scheduled contact** must be recorded on the AE CRF page and reported to the sponsor according to the reporting procedures outlined in [Section 5.3](#). All SAEs that are ongoing at the last scheduled contact will be recorded as ongoing on the CRF.

This may include **unresolved previously reported SAEs, or new SAEs**. The investigator will follow SAEs until the events are resolved, stabilized, or the subject is lost to follow-up. The investigator will continue to report any significant follow-up information to the sponsor until the event is resolved, stabilized, or the subject is lost to follow-up with the IRE form.

5.7.3 Follow-up and Reporting of Serious Adverse Events Occurring After Last Scheduled Contact

Any new SAEs reported by the subject to the investigator that occur **after the last scheduled contact**, and are determined by the investigator to be reasonably associated with the use of the IMP, should be reported to the sponsor. This may include SAEs that are captured on follow-up telephone contact or at any other time point after the defined trial period (ie, up to last scheduled contact). The investigator should follow SAEs identified after the last scheduled contact until the events are resolved, stabilized, or the subject is lost to follow-up. The investigator should continue to report any significant follow-up information to the sponsor until the event is resolved, stabilized, or the subject is lost to follow-up with the IRE form.

Protocol 156-102-00136

6 Pharmacokinetic/pharmacodynamic Analysis

6.1 Pharmacokinetic Analysis

6.1.1 Primary Variables

AUC_t and C_{max} of tolvaptan

6.1.2 Reference Variables

- 1) Plasma concentration-time profile of tolvaptan
- 2) AUC_∞, MRT_∞, t_{max}, λ_z, AUC_%Extrap, t_{1/2,z}, CL/F, CL/F/BW, and t_{last} of tolvaptan
- 3) By-subject ratios of AUC_t, C_{max}, AUC_∞, MRT_∞, and λ_z of tolvaptan for administration of OD tablet with and without water to those for administration of conventional tablet
- 4) Difference (value for OD tablet minus value for conventional tablet) in t_{max} by subject between administration of OD tablet without water and administration of conventional tablet and between administration of OD tablet with water and administration of conventional tablet

6.1.3 Datasets for Analysis

The datasets for analysis are the same as that specified in [Section 7.2.2, Bioequivalence Analysis Set](#).

6.1.4 Calculations of PK Parameters

- 1) AUC_t, C_{max}, AUC_∞, MRT_∞, t_{max}, λ_z, AUC_%Extrap, t_{1/2,z}, t_{last}, and CL/F are to be calculated per subject by non-compartmental analysis.
- 2) Actual time after each IMP administration will be used in the calculations.
- 3) The value 0 will be imputed for each plasma drug concentration measurement below the lower limit of quantitation in the calculations of PK parameters and descriptive statistics. For calculation of λ_z from each blood sampling time point after t_{max}, a measurement below the lower limit of quantitation will be treated as missing.
- 4) CL/F/BW is to be calculated by dividing CL/F by body weight (kg) before IMP administration in each period.
- 5) The ratio between the formulations and regimens is to be calculated per parameter in each subject by [Value after dosing of OD tablet without water] / [Value after dosing of conventional tablet] and [Value after dosing of OD tablet with water] / [Value after dosing of conventional tablet] (parameters, AUC_t, C_{max}, AUC_∞, MRT_∞, and λ_z).

Protocol 156-102-00136

6) Differences in t_{\max} ($[t_{\max}]$ after dosing of OD tablet without water) – ($[t_{\max}]$ after dosing of conventional tablet) and also ($[t_{\max}]$ after dosing of OD tablet with water) – ($[t_{\max}]$ after dosing of conventional tablet)) are to be calculated per subject.

6.1.5 Calculation of Descriptive Statistics

Descriptive statistics of the parameter specified in 1) of [Section 6.1.2](#) are to be calculated per blood sampling time point by cohort and regimen (conventional tablet, OD tablet without water, and OD tablet with water). For each parameter listed in 2) of [Section 6.1.2](#), descriptive statistics are to be calculated by cohort and regimen (conventional tablet, OD tablet without water, and OD tablet with water).

6.2 Pharmacodynamic Analysis

No pharmacodynamic analysis is planned.

7 Statistical Analysis

7.1 Sample Size

With reference to the Guidelines for Bioequivalence Studies of Generic Products,¹ the sample size for this study was calculated as the number of subjects required to demonstrate that the 90% confidence intervals of the geometric mean ratios of the AUC_t and C_{\max} of tolvaptan (OD tablet without water vs conventional tablet and OD tablet with water vs conventional tablet) fall inside the bioequivalence range of $\ln(0.8)$ to $\ln(1.25)$.

Of the prior crossover studies of tolvaptan in healthy adults, Study 156-00-002 reported the largest intra-individual variability (AUC_t and C_{\max} , 0.033 and 0.056, respectively). Sample size calculation was performed using the method proposed by Diletti, et al. (1991)⁵ based on the C_{\max} , in which intra-individual variability was large.

When the ratio of the expected C_{\max} with the tolvaptan OD tablet (administered with or without water) to that with the tolvaptan conventional tablet is assumed to be 1.05, at least 12 subjects per group are required to achieve a power of at least 90%. To account for withdrawals and dropouts, the sample size for this study was set to 14 subjects per group for 1 cohort, for a total of 42 subjects.

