3.7.1.4.3 Subject Replacement (Only on Day 1)

Each enrolled subject who withdraws consent or is judged not to be able to receive IMP before the start of IMP administration will be replaced with a reserve subject.

Neither subject enrollment nor replacement will take place for discontinued subjects after IMP administration.

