7.2.2 Bioequivalence Analysis Set

The bioequivalence analysis set will include all subjects with both AUC_t and C_{max} values across Period 1, 2, and 3.

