7.4.1 Primary Variable Analysis

- 1) For the AUC_t and C_{max} of tolvaptan, data will be log-transformed and analysis of variance (ANOVA) will be performed using group (group receiving conventional tablet first, group receiving OD tablet without water first, and group receiving tolvaptan OD tablet with water first), formulation and dosing regimen, subjects within group, and administration period (Period 1, Period 2, and Period 3) as factors. The analysis will use natural logarithms.
- 2) For the AUC_t and C_{max} of tolvaptan, the 90% confidence intervals (CIs) of the ratio of the geometric mean values for the 2 formulations (OD tablet without water vs conventional tablet and OD tablet with water vs conventional tablet) will be calculated. Bioequivalence between the formulations and between the dosing regimens is to be demonstrated when the 90% confidence intervals fall inside the range of $\ln(0.8)$ to $\ln(1.25)$. Bioequivalence between the OD tablet and conventional tablet is to be established when the bioequivalence criteria are met between the OD tablet administered without water and conventional tablet and also between the OD tablet administered with water and conventional tablet. When an add-on subject study is conducted, bioequivalence is to be assessed in the same manner using the pooled data of both the main study and add-on subject study.
- 3) When there are subjects without evaluable parameters across Periods 1, 2, and 3, sensitivity analysis including those subjects will be performed.

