9.4.1.2 In the Event Vomiting Occurs

With reference to the Food and Drug Administration (FDA) guidance,³ if vomiting occurs at a time point less than twice the median t_{max} , the data for this period for the subject who experienced vomiting will be excluded from pharmacokinetic analysis. The median t_{max} that is referenced for that judgment is the median of the same group in the same study calculated excluding the vomiting case.

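### The 90% power stated for 12 per group belongs to a single Cmax comparison; under the plan's four-interval rule it is about 86–87%, so the dropout margin is about 2 subjects per cohort, not 6

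*Protocol*

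**What the plan says.** Protocol 7.1, repeated in SAP 4, defines the sample size as the number needed for "the 90% confidence intervals of the geometric mean ratios" of AUCt and Cmax to fall between ln(0.8) and ln(1.25), for both OD regimens against the conventional tablet. The calculation uses Cmax, the more variable endpoint, with intra-individual variability 0.056 (0.033 for AUCt) and an expected ratio of 1.05. Its result is that "at least 12 subjects per group are required to achieve a power of at least 90" percent. It continues: "To account for withdrawals and dropouts, the sample size for this study was set to 14 subjects per group for 1 cohort", which makes 42 per cohort.

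The decision rule is in protocol 7.4.1 (SAP 9.1): "Bioequivalence between the OD tablet and conventional tablet is to be established when the bioequivalence criteria are met between the OD tablet administered without water". That sentence goes on to name the conventional tablet as comparator and to make the with-water comparison a second condition that must hold too. With two endpoints, that is four intervals per cohort.

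Three provisions determine how many subjects count:
- Protocol 7.2.2: "The bioequivalence analysis set will include all subjects with both" AUCt and Cmax in all three periods.
- Protocol 3.7.1.4.3: "Neither subject enrollment nor replacement will take place for discontinued subjects after IMP administration".
- SAP 9.4.1.2, on early vomiting: "the data for this period for the subject who experienced vomiting will be excluded from pharmacokinetic analysis".

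**The concern.** The goal and the decision rule need four intervals to succeed together. The power statement follows directly on that goal, but its inputs describe one comparison on one endpoint. Basing the size on the more variable endpoint largely deals with AUCt. It does not deal with the second Cmax comparison, which has the same variance and the same assumed ratio and must also pass.

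A reader of 7.1 would conclude that a cohort can fall from 42 to 36 evaluable subjects and keep at least 90% power for the bioequivalence decision. The plan makes each loss expensive: a dosed subject is not replaced, and one missing or excluded period removes the whole subject from the primary analysis set. If the true tolerance is smaller than the text implies, the sponsor may misjudge how a cohort stands after a few losses.

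**Working it through.** **Inputs from the documents (protocol 7.1, 7.4.1).** Limits ±ln(1.25) = ±0.2231; 90% intervals, so 5% per side; Cmax variability 0.056 and AUCt 0.033; true Cmax ratio 1.05, ln(1.05) = 0.0488; 36 or 42 subjects per cohort.

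**Inputs assumed.** The values 0.056 and 0.033 are log-scale intra-subject variances. The AUCt ratio is 1.00 to 1.05. The AUCt–Cmax residual correlation is 0 to 0.8. Only the main study is counted.

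**Step 1: reproduce 12 per group.** For one comparison with n complete subjects, SE = √(2σ²/n). At n = 36, SE = √(2 × 0.056/36) = 0.0558. The nearer limit is 0.2231 − 0.0488 = 0.1744 away, or 0.1744/0.0558 = 3.13 standard errors. Exact two-one-sided-tests power for one Cmax comparison:

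| n | df = n − 2 | df = 2n − 4 |
|---|---|---|
| 33 | 89.8% | 90.4% |
| 34 | 90.7% | 91.2% |
| 36 | 92.1% | 92.6% |
| 42 | 95.3% | 95.6% |

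With the two-period crossover df (n − 2), 90% is first reached at 34, which rounds up to 36 in three equal groups: the stated 12 per group. Reading 0.056 as a standard deviation fails, because 5 subjects in total would then already give 97.5%. The variance reading is therefore the one that fits.

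**Step 2: joint power under the plan's rule.** The ANOVA in 7.4.1 has 3n observations. Its residual df is 3n − 1 − 2 (group) − (n − 3) (subjects within group) − 2 (period) − 2 (treatment) = 2n − 4. Both OD comparisons subtract the same conventional-tablet mean, so each difference has variance 2σ²/n, their covariance is σ²/n and their correlation is 0.5. They also share one residual variance estimate. Joint power was simulated with 1,000,000 runs per setting; residual variances were drawn from a Wishart distribution. The last column spans the assumed AUCt ratios and correlations:

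| Evaluable n | One Cmax interval | Both Cmax intervals | All four intervals |
|---|---|---|---|
| 36 | 92.6% | 87.3% | 85.9–87.2% |
| 39 | 94.2% | 90.0% | 89.1–90.0% |
| 40 | 94.7% | 90.8% | 90.0–90.8% |
| 42 | 95.6% | 92.2% | 91.6–92.2% |

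**Step 3: where the loss comes from.** At 36, requiring both Cmax comparisons takes power from 92.6% to 87.3%. AUCt takes at most about 1.4 points more (87.3 − 85.9). Most of the shortfall therefore does not depend on the unstated AUCt inputs.

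**Step 4: the margin.** The nominal allowance is 42 − 36 = 6. All-four power reaches 90% at 40 evaluable, so 42 − 40 = 2 subjects are spare. A third is spare only if the AUCt ratio is near 1.00 or the correlation is near 1.

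**Step 5: sensitivity at 36.** A Cmax variance of 0.050 (AUCt scaled alike) gives 90.2–90.8%. Ratios of 1.04 give 89.8–90.4%. Cmax ratios on opposite sides of 1 (1.05 and 1/1.05; AUCt ratio 1.00, correlation 0.8) give 85.3%, and 91.2% at 42.

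**The case against.** The strongest reply is that nothing in 7.1 is miscalculated. Twelve per group is right for the calculation described, the Cmax basis is disclosed, and the enrolled 42 exceeds 90% for the full rule. This stands, and it is why no change to the trial is proposed. What 7.1 does not disclose is that the power covers one comparison, and the sentence stating the goal points to four.

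Protocol 7.7 also provides an add-on study when the sample proves insufficient. Simulating 36 evaluable subjects followed, on failure, by a pooled analysis with 18 to 21 more gives overall power of about 97.5–98.1%. That is an upper figure: it assumes the add-on is always run when permitted, while 7.7 says only that it may be. It softens the consequence, but 7.1 sizes the main study, and its figure is read as main-study power.

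The remaining points are fair on size. The variance is the largest from the prior crossover studies, so the input is cautious. The boundary moves by about one subject with the choice of df: with n − 2 throughout, all-four power at 40 is 89.4–90.2%. Large losses are not obviously expected in healthy men confined to the site, and partial data enter the mixed-model sensitivity analysis in SAP 9.1, though not the primary one. These points make the shortfall modest. They do not make the stated figure apply to the stated goal.

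**Conclusion.** The concern holds. The power of at least 90% at 12 per group is correct for one Cmax comparison and is not the power of the decision rule, which is about 3 to 4 points below 90% at 36 evaluable subjects. The planned 42 gives about 92% for the full rule, so the design is adequately sized, with a tolerance of about 2 non-evaluable subjects per cohort (3 under favourable assumptions) rather than 6.

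The conclusion rests on the variance reading of 0.056 and 0.033, which reproduces the plan's figure, on the stated ratio of 1.05 and on main-study power alone. It is sensitive to these inputs: a variance of 0.050 or ratios of 1.04 bring 36 subjects to about 90%. The consequence is for planning and reporting only.

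**What to change.** Restate the power in protocol 7.1 and SAP 4, for example:

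> Assuming log-scale intra-subject variances of 0.056 (Cmax) and 0.033 (AUCt) and a true ratio of 1.05, 14 evaluable subjects per group give about 92% power for all four 90% confidence intervals in a cohort. Twelve evaluable per group give about 93% power for one Cmax comparison and about 86–87% for all four. Power for all four stays at or above about 90% with up to about 2 non-evaluable subjects per cohort.

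The text should add that these are main-study figures, and state the residual df and the AUCt–Cmax correlation range used, because the boundary shifts by about one subject with those choices. The cost is wording in two sections and a slightly less favourable stated figure at 12 per group.

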7.2 Datasets for Analysis

7.2.1 Safety Analysis Set

The safety analysis set will include all subjects that were administered at least one dose of IMP.

Protocol 156-102-00136

7.2.2 Bioequivalence Analysis Set

The bioequivalence analysis set will include all subjects with both AUC_t and C_{max} values across Period 1, 2, and 3.

7.3 Handling of Missing Data

Missing values will not be imputed.

7.4 Primary and Reference Endpoint Variables

The following analyses will be performed for the bioequivalence analysis set per cohort.

7.4.1 Primary Variable Analysis

- 1) For the AUC_t and C_{max} of tolvaptan, data will be log-transformed and analysis of variance (ANOVA) will be performed using group (group receiving conventional tablet first, group receiving OD tablet without water first, and group receiving tolvaptan OD tablet with water first), formulation and dosing regimen, subjects within group, and administration period (Period 1, Period 2, and Period 3) as factors. The analysis will use natural logarithms.
- 2) For the AUC_t and C_{max} of tolvaptan, the 90% confidence intervals (CIs) of the ratio of the geometric mean values for the 2 formulations (OD tablet without water vs conventional tablet and OD tablet with water vs conventional tablet) will be calculated. Bioequivalence between the formulations and between the dosing regimens is to be demonstrated when the 90% confidence intervals fall inside the range of $\ln(0.8)$ to $\ln(1.25)$. Bioequivalence between the OD tablet and conventional tablet is to be established when the bioequivalence criteria are met between the OD tablet administered without water and conventional tablet and also between the OD tablet administered with water and conventional tablet. When an add-on subject study is conducted, bioequivalence is to be assessed in the same manner using the pooled data of both the main study and add-on subject study.
- 3) When there are subjects without evaluable parameters across Periods 1, 2, and 3, sensitivity analysis including those subjects will be performed.

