2.2 Dosing Rationale

2.2.1 Regimens

The 2000 Guidebook for Approval Application for Pharmaceutical Products² states “For the application for approval of a new OD tablet following the approval of a conventional tablet formulation, a ‘bioequivalence study comparing (the conventional tablet administered with water) with (the proposed formulation administered without water)’ and another ‘bioequivalence study comparing (the conventional tablet administered with water) with (the proposed formulation administered with water)’ are in principle recommended to characterize the OD tablet.” This is the reason for the intended regimens with and without water. The Guidelines for Bioequivalence Studies of Generic Products¹ stipulate “In principle, drugs are given to subjects with 100 to 200 mL water (normally 150 mL) after fasting for more than 10 hours.” This is the rationale for the selected volume (about 150 mL) of water to be used for administration with water.

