7.7 Decision on Whether to Conduct an Add-on Subject Study

When bioequivalence is not demonstrated due to insufficient samples in the main study, an add-on subject study in additional subjects may be conducted once in accordance with the procedures of the main study. When bioequivalence is demonstrated in only one of the cohorts, an add-on subject study will be conducted in the cohort in which bioequivalence is not demonstrated.

The add-on subject study must enroll at least half the number of subjects enrolled in the main study. An add-on subject study will not be conducted when:

- 1) When the point estimates of the differences in mean log-transformed AUC_t and C_{max} between the conventional tablet and OD tablet do not fall inside the range of $\ln(0.8)$ to $\ln(1.25)$ in the main study; or
- 2) The sample size calculated from the results of the main study for the add-on subject study is ethically inappropriate and/or not scientifically feasible.

When data from the add-on subject study are pooled with those of the main study for analysis, the study will be included as a variation factor in the analysis.

8 Management of Investigational Medicinal Product and Reference Product

Tolvaptan OD tablet 15 mg and tolvaptan OD tablet 30 mg are the test products and provided to this study as IMPs. Tolvaptan conventional tablet 15 mg and tolvaptan conventional tablet 30 mg will be used as the reference products.

For full details on Management of the IMPs and reference products, please refer to the IB and Clinical Operation Manual.

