3.4 Handling of Time Points

Data measured at the time points specified in the protocol will be used. Examinations specified for discontinuation and unscheduled examinations will be presented in lists, but will not be used in summaries.

4 Sample Size

With reference to the Guidelines for Bioequivalence Studies of Generic Products,¹ the sample size for this study was calculated as the number of subjects required to demonstrate that the 90% confidence intervals of the geometric mean ratios of the AUC_t and C_{max} of tolvaptan (OD tablet without water vs conventional tablet and OD tablet with water vs conventional tablet) fall inside the bioequivalence range of $\ln(0.8)$ to $\ln(1.25)$.

Of the prior crossover studies of tolvaptan in healthy adults, Study 156-00-002 reported the largest intra-individual variability (AUC_t and C_{max} , 0.033 and 0.056, respectively). Sample size calculation was performed using the method proposed by Diletti, et al. (1991)² based on the C_{max} , in which intra-individual variability was large.

When the ratio of the expected C_{max} with the tolvaptan OD tablet (administered with or without water) to that with the tolvaptan conventional tablet is assumed to be 1.05, at least 12 subjects per group are required to achieve a power of at least 90%. To account for withdrawals and dropouts, the sample size for this study was set to 14 subjects per group for 1 cohort, for a total of 42 subjects.

5 Statistical Analysis Sets

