9.4.2 Reporting of Concentrations and Parameters

- 1) Values below the lower limit of quantitation occurring at time points before the first quantified level for drug concentration will be treated as 0.
- 2) Values below the lower limit of quantitation occurring at time points after the first quantified level for drug concentration will be treated as missing.
- 3) Descriptive statistics for parameters listed in [Section 6.2](#) 1) will be calculated at each blood collection point, for each cohort, for administration of the conventional tablet, OD tablet without water, and OD tablet with water. Descriptive statistics for parameters listed in [Sections 6.1](#) and [6.2](#) 2) will be calculated for each parameter, for each cohort, for administration of the conventional tablet, OD tablet without water, and OD tablet with water. The descriptive statistics calculated for plasma drug concentration will be number of subjects, arithmetic mean, standard deviation, coefficient of variation, minimum, median, and maximum, the descriptive statistics calculated for parameters other than t_{max} and t_{last} will be number of subjects, arithmetic mean, standard deviation, coefficient of variation, geometric mean, minimum, median, and maximum, and the descriptive statistics calculated for t_{max} and t_{last} will be number of subjects,

minimum, median, and maximum. Descriptive statistics will not be calculated for λ_z (Rsq), λ_z (point), λ_z (upper), or λ_z (lower).

- 4) Arithmetic means and standard deviations will be used to plot plasma concentration-time profile.
- 5) Individual values and descriptive statistics for pharmacokinetic parameters are displayed using the number of digits presented in [Table 9.4.2-1](#). Coefficient of variation (CV%), which is used as a descriptive statistic, will be rounded off to 1 decimal place.

Table 9.4.2-1 Handling of Numerical Values	
AUC _t , AUC _∞	3 significant figures
AUC% Extrap	1 decimal place
C _{max}	3 significant figures
CL/F, CL/F/BW	3 significant figures
MRT _∞	1 decimal place
t _{max}	1 decimal place
t _{last}	1 decimal place
t _{1/2,z}	1 decimal place
λ_z	3 significant figures
λ_z (point)	Whole numbers
λ_z (lower), λ_z (upper)	2 decimal places
λ_z (Rsq)	4 decimal places
Geometric mean ratio (GMR)	4 decimal places
Confidence interval of GMR	4 decimal places
By-subject ratio	2 decimal places
Difference in t _{max} by subject	1 decimal place

10 Pharmacodynamic Analysis

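### Does the primary acceptance rule judge a ratio on log-scale limits, and claim equivalence between dosing regimens that no interval tests?

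*Protocol*

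**What the plan says.** Protocol 7.4.1 first specifies an ANOVA of log-transformed AUCt and Cmax, using natural logarithms. Its second item calls for "90% confidence intervals (CIs) of the ratio of the geometric mean values for the 2 formulations" and names two: OD without water against conventional, and OD with water against conventional. The acceptance rule follows ("Bioequivalence between the formulations and between the dosing regimens is to be demonstrated when the 90% confidence intervals fall inside the range of"), with limits ln(0.8) and ln(1.25). The next sentence concludes that the OD and conventional tablets are bioequivalent when both named comparisons meet the criteria. SAP 9.1(2) carries the same text.

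The sample-size sections pair a ratio with the same log limits. Protocol 7.1 seeks "the number of subjects required to demonstrate that the 90% confidence intervals of the geometric mean ratios of the" two primary variables within ln(0.8) to ln(1.25), and SAP Section 4 agrees ("required to demonstrate that the 90% confidence intervals of the geometric mean ratios of the").

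Elsewhere the scale is explicit. The add-on rule in Protocol 7.7 sets "the point estimates of the differences in mean log-transformed" AUCt and Cmax against these limits. SAP 9.1(3) states its contrasts as differences. SAP Table 9.4.2-1 gives a display format for "Confidence interval of GMR".

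On regimens, Protocol 2.2.1 justifies the two ways of giving the OD tablet ("This is the reason for the intended regimens with and without water"). Protocol 6.1.4 says "The ratio between the formulations and regimens is to be calculated per parameter in each subject by" OD without water over conventional and OD with water over conventional, and lists no other ratio.

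**The concern.** The sentence decides pass or fail for the primary variables, so its wording matters more than most. Two things look wrong.

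- **Scale.** An interval for a ratio is always positive. Limits of -0.223 to 0.223 belong to a difference in log means. Taken literally, the rule is not the usual equivalence criterion, and the SAP does not repair it.
- **Regimens.** The rule announces equivalence between dosing regimens, and the protocol elsewhere uses regimen for giving the OD tablet with or without water. Two passes against the conventional tablet do not imply that the two OD conditions are equivalent to each other. A report that said so would state something untested.

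**Working it through.** **Inputs.** Limits: ln(0.8) = -0.2231 and ln(1.25) = 0.2231 (Protocol 7.4.1). Cmax intra-individual variability 0.056, expected ratio 1.05, power at least 90%, 12 per group needed and 14 per group planned, so 36 and 42 per cohort (Protocol 7.1). The documents do not label 0.056; it is taken here as a log-scale variance.

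**1. Reproduce the plan's sample size.** Use two one-sided 5% tests on the log difference, with limits ±0.2231 and SE = √(2 × 0.056 / N).
- With N - 2 degrees of freedom (two-way crossover), the smallest even N reaching 90% is 34 (power 90.6%). Rounded up to a multiple of 3 this is 36, or 12 per group (power 92.1%).
- With 2N - 4 degrees of freedom (this three-period model), power at 36 is 92.6%.
- With 0.056 read as an SD, power is already about 100% at N = 24, so that reading does not give 12 per group.

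The plan's figure therefore comes from log differences judged against log limits.

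**2. Literal against intended scale, Cmax, n = 42.** Degrees of freedom = 2 × 42 - 4 = 80. Half-width = 1.664 × √(2 × 0.056 / 42) = 0.0859.

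| Observed ratio | 90% CI, log scale | 90% CI, ratio scale | Intended rule | Literal rule |
|---|---|---|---|---|
| 1.00 | -0.086 to 0.086 | 0.918 to 1.090 | pass | fail |
| 1.05 | -0.037 to 0.135 | 0.964 to 1.144 | pass | fail |

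Under the literal rule only an upper limit below 0.2231 can bind, which needs an observed ratio below 0.2231 × exp(-0.0859) = 0.205. The rule would reject identical products and accept a tablet giving about a fifth of the reference Cmax. The log interval within ±0.2231 and the ratio interval within 0.80 to 1.25 are the same test, so either display leads to the same decision.

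**3. What the regimen phrase can refer to.**
- The intervals in the rule are the two named in the preceding sentence, and the sentence after it uses only those two.
- The synopsis gives the comparator its own dosing regimen, with about 150 mL of water. OD without water against conventional therefore already compares two regimens as well as two formulations.
- The objective (Protocol 2.3), the by-subject ratios and tmax differences (Protocol 6.1.4, SAP 9.3.2), the add-on rule (Protocol 7.7) and the sensitivity analysis (SAP 9.1(3)) contain no OD-versus-OD contrast.

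**4. How far the two OD conditions could differ, n = 42.** The largest passing absolute log ratio is 0.2231 - 0.0859 = 0.1372, so observed ratios of 0.872 and 1.147 both just pass. Their quotient is exp(2 × 0.1372) = 1.316, with 90% CI 1.207 to 1.434. Simulated frequencies (variance 0.056, independent residuals):

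| True ratios to conventional | n | Both planned intervals pass | Both pass, OD-versus-OD interval fails |
|---|---|---|---|
| 1.05 and 1.05 | 42 | 92% | 0.5% |
| 1.05 and 1.05 | 36 | 87% | 1.1% |
| 1.05 and 1/1.05 | 42 | 91% | 16.5% |
| 1.05 and 1/1.05 | 36 | 85% | 18.2% |

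The first two rows use the plan's assumption of 1.05 with or without water. The last two are a stress case that the documents do not assume.

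**The case for a change.** The case for rewording is fair. The mismatch appears in four places, Protocol 7.7 shows the authors could write the matched form, and one sentence in each place would cure it at no analytic cost. The filing rests on this criterion (Protocol 2.1). On regimens, Protocol 6.1.5 treats regimen as three levels, and the synopsis lists formulation and dosing regimen as separate factors. With only three treatment cells, a separate regimen effect would be exactly the OD with-versus-without contrast. If the two conditions truly lay on opposite sides of the reference, as in the stress case, 18% (n = 42) to 21% (n = 36) of trials passing both planned intervals would fail an OD-versus-OD one.

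What stands is that the notation is loose, and that passing both planned comparisons does not prove the two OD conditions equivalent to each other. The rest does not carry. Two separate two-level factors and one three-level factor both use 2 degrees of freedom over the same three cells, so the fitted model is the same. The synopsis still asks for only the two intervals against conventional, and the three-level use in 6.1.5 only organises descriptive tables. The stress-case figures measure the error in a claim that no section of either document plans to make.

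**Conclusion.** No change follows. The scale point is a clerical slip: log-scale limits are attached to the name of the back-transformed quantity. The log analysis, the add-on rule and the reproduced 12 per group all fix the intended criterion, and an analyst would apply it without hesitation. The regimen phrase is loose wording for two comparisons that differ in formulation, or in formulation and water, and the following sentence limits the conclusion to OD against conventional.

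Rewording would leave every number as it is: the two contrasts, the decision, 36 evaluable and 42 enrolled per cohort, and power of about 92% to 93% per Cmax contrast at 36. Adding a third required interval would answer a question outside the objective and would lower joint Cmax power slightly, from 92.1% to 91.6% at 42 and from 87.2% to 86.2% at 36, with both true ratios at 1.05.

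The power and interval figures rest on 0.056 being a log-scale variance, the only reading tried that reproduces the stated sample size. The reading of the two sentences does not depend on it.
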